4.2 Analysis of the primary outcome

The analysis for comparing the counts between the control and the intervention arms will be done using a GLMM (*Ime4* package, *Imer* function in R) with Poisson distribution using log link function, where a cluster will be specified as a random factor (i.e. random intercept) and recruitment time by

QMS Form number: FM-06-02-	CONFIDENTIAL	Page 14 of 26
05/v2.0		

FIND	Statistical Analysis Plan		
Protocol number:	TB041-3/1-TAN / -MOZ		
Document version:	5.0	Document date:	11-JUL-2023

clinic will be specified as a random effect nested within each cluster (i.e. random intercept and random slope).

The analysis for comparing the proportions between the control and the intervention arms will be done using a GLMM (*Ime4* package, *Imer* function in R) with binomial distribution using logit link function, where a cluster will be specified as a random factor (i.e. random intercept).

The models will be adjusted for gender, age, HIV status, country, and asset index that is described below. In case of necessity, the models may be adjusted for the setting (i.e. urban, rural, peri-rural nesting the clusters), and site.

ORs will be estimated by calculating the exponent of the fixed-effect (i.e. arm) coefficients that are extracted from the models described above. 95% confidence intervals will be calculated using Wald method.

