A cluster randomized controlled trial to evaluate the effect of placing Truenat platform/TB assays at primary health care clinics combined with rapid communication of results on time to treatment initiation of microbiologically confirmed TB. In a setup period (survey of study centers) before randomization, the healthcare facilities (=clinics) of 4 sites will be asked to provide information about the number of TB notifications per quarter covering the period 1/2018-6/2020. From this information the foreseeable number of examined patients ("size of a clinic") will be derived, which will be used as a strata variable in randomization process.

Facilities will be randomly allocated to the standard of care (control), or Truenat platform/TB assays. A cluster refers to a

	EDCTP
	clinic. The clusters will be assigned to intervention or control arm to one of two diagnostic procedures (SOC [smear microscopy and/or Xpert MTB/RIF Ultra off-site] vs Truenat platform/TB assays on-site) following a restricted randomization strategy, whereby 6 to 8 strata of clusters will be established using the stratification variables site (clinics belong to a site) and size and apply balance criteria for them. The number of strata per site depends on heterogeneity of the sizes of the clinics as established in setup period and may be increased, typically 1 or 2 strata per site will be established. The primary endpoint will be compared in an individual level analysis with strata and intervention as fixed effects and cluster as random effect.
Population	A total of 29 clinics will be randomized at the four participating sites aiming to enrol up to 150 adults (≥ 18 years of age) each (total approximately 4200) with signs and symptoms suggestive of TB. The number of clinics might be extended up to 37 due to the information gained in the setup period. Dependent on the loss to follow-up at 7 days, recruitment may need to be extended.
Inclusion/Exclusion Criteria (Site)	Based on information gained in the setup period sites will be included in the randomization process using the following criteria: Inclusion Criteria: Provision of TB treatment at the clinic Availability of electricity Willingness to participate Exclusion criteria: Patients with TB referred for treatment to other sites Sites with less than 10 patients registered for TB treatment per quarter

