	 Absolute number and point estimate (with 95% CIs) of the proportion of enrolled participants evaluated for pulmonary TB starting TB treatment regardless of microbiological confirmation within 7 and 60 days from enrolment Estimate of time to TB treatment initiation for those with microbiological confirmation and for all participants (censored at 60 days) from enrolment Point estimate of the proportion of patients with ongoing treatment (on treatment) among: Participants diagnosed with TB either clinically or with microbiological confirmation Participants clinically diagnosed with TB Participants with microbiological confirmation of TB

Morbidity related endpoints:

 Prevalence of current cough, limited appetite, weakness at 60 days from enrolment

Cost and productivity related endpoints:

• Patients' costs related to care

Additional endpoints:

Operational characteristics:

- Truenat platform / TB assay non-determined test results rates
- Rate of Truenat platform failure

Statistical Considerations

Randomization:

Restricted randomization approach resulting in 6 to 8 strata applying factors site and size of the clusters (=clinics). The strata are constructed using variables site and size of the clinic, whereby appropriate coarsening of the size and balance criteria are applied. The number of strata may be increased in case of heterogeneity of sizes of the clusters (as indicated by information gained in setup period)

Description:

Baseline characteristics, such as demographic and analytical data will be summarized using descriptive statistical methods.

Continuous data will be summarized using the mean, the median, standard deviation, the range (minimum and maximum value).

Categorical values will be summarized using frequency counts and percentages.

Analysis:

Individual level analysis using generalized linear mixed model (GLMM) with logit link function, intervention (y/n) and stratum as fixed effects and cluster as a random effect.

Sensitivity analyses based on cluster-level summaries will be applied. Adjustment for other variables (such as HIV status) may be considered in sensitivity analyses and will be described in detail in the statistical analysis plan (SAP).

Sample size:

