9.6.1 Primary endpoint

The primary endpoint is the estimate of the number and proportion of participants with microbiological confirmation starting TB treatment within 7 days of their first visit among enrolled participants.

Protocol Version: 4.0 - CONFIDENTIAL - Page 32 of 57

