2.1 Primary endpoint

The primary outcome of the study is the absolute number and point estimate (with 95% CIs) of the proportion of participants with TB microbiological confirmation starting TB treatment within 7 days of their first visit. We evaluate the probability of the patients in the intervention arm (with Truenat) for a favourable outcome of interest compared to patients in the SOC arm as a binary outcome of success or failure.

The hypotheses of interest are:

and,

 ${\it H0}:$ Number of successes in intervention arm is same as in the SOC arm.

H1: Number of successes in intervention arm is different from the SOC arm

H0: Proportion of success in intervention arm is same as in the SOC arm.

H1: Proportion of success in intervention arm is different from the SOC arm

This is translated in terms of odds ratio (OR) for odds of success in the intervention arm to be different from the odds of success in the SOC arm thus leading to the definition of the following hypothesis:

QMS Form number: FM-06-02-	CONFIDENTIAL	Page 6 of 26
05/v2.0		-

FIND >>>	Statistical Analysis Plan		
Protocol number:	TB041-3/1-TAN / -MOZ		
Document version:	5.0	Document date:	11-JUL-2023

 $H0: OR_{Intervention:SOC} = 1 \text{ vs. } H1: OR_{Intervention:SOC} \neq 1$

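### The primary count model reports a log-link ratio as an odds ratio; it also states no row unit or offset, so a fit to aggregated rows would pick up enrolment differences

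*SAP*

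**What the plan says.** Protocol 9.6.1 defines the primary endpoint as "the number and proportion of participants with microbiological confirmation starting TB treatment within 7 days of their first visit among enrolled participants". SAP 2.1 sets one null for each part. The first is "Number of successes in intervention arm is same as in the SOC arm", the second is the same statement for the proportion, and both are then expressed as an odds ratio of 1.

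SAP 4.2 gives each part its own model. The proportion has a binomial logit model with a random intercept for cluster. The count has a mixed model "with Poisson distribution using log link function, where a cluster will be specified as a random factor (i.e. random intercept) and recruitment time by" "clinic will be specified as a random effect nested within each cluster (i.e. random intercept and random slope". No row unit, offset, exposure or denominator is given for the count model. For both models, "The models will be adjusted for gender, age, HIV status, country, and asset index that is described below", and "ORs will be estimated by calculating the exponent of the fixed-effect (i.e. arm) coefficients that are extracted from the models described above".

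The Protocol describes only the proportion model: "The primary endpoint will be compared in an individual level analysis with strata and intervention as fixed effects and cluster as random effect" (synopsis, Study Design) and "Individual level analysis using generalized linear mixed model (GLMM) with logit link function" (synopsis, Statistical Considerations).

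SAP 4.3 carries the Poisson and binomial pair over to the secondary endpoints. SAP 8 (Bias reduction) recognises that intervention clinics may recruit faster. It plans continuous monitoring, with clinic-level investigation if the arms differ by more than 5%.

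**The concern.** There are two separate matters.

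**The label.** Exponentiating an arm coefficient gives an odds ratio under a logit link only. Under a log link it gives a ratio of expected counts, which is a rate or risk ratio. SAP 4.2 applies one label to both models.

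**The unit of analysis.** Two analysts following SAP 4.2 could fit models that answer different questions. With one 0/1 row per participant, the count model compares risks. With one total per clinic or clinic-period and no offset, it compares yields, and yield depends on how many people were enrolled as well as on how many of them were diagnosed and treated. The count null could then be rejected because one arm enrolled more or faster, with equal proportions treated. The recruitment-time term does not prevent this. A random effect with mean zero describes variation between clinics around the arm mean. A systematic difference between arms stays in the arm coefficient. An offset instead enters with its coefficient fixed at 1.

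**Working it through.** **Reproducing the planned figures.** Inputs from SAP 8, selected scenario: prevalence 12%; sensitivity 89% and 70%; diagnostic loss 2% and 10%; pre-treatment loss 10% and 20%; cluster size 150; coefficient of variation (CV) 0.25.

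- p_i = 0.12 × 0.89 × 0.98 × 0.90 = 0.0942
- p_c = 0.12 × 0.70 × 0.90 × 0.80 = 0.0605
- Cluster pairs = A + 7.849 × (0.000569 + 0.000379 + 0.000783) / 0.0337² = A + 11.95

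With A = 1 (Protocol 13.8) this is 12.95, rounded up to the stated 13. The SAP writes A = 2, which would give 14. That does not affect this point.

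**Size of the label error.** Risk ratio = 0.0942 / 0.0605 = 1.557. Odds ratio = (0.0942/0.9058) / (0.0605/0.9395) = 1.615. The gap is 1.615/1.557 = 1.037, about 4%. Across prevalence 12-20% and control sensitivity 70-80%, with the other inputs as above, the risk ratio is 1.36-1.56 and the odds ratio 1.40-1.66. Both equal 1 under the null, so the test does not change.

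**Participant rows.** Take a clinic with n participants, common mean μ and Y successes. Summing the Poisson terms over its 0/1 rows gives Y log μ − nμ. Apart from a constant, this is the likelihood of the clinic total Y with offset log n (no person-level covariates). The arm coefficient is a log risk ratio, and with equal proportions the ratio is 1 whatever the enrolment.

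**Aggregated rows, no offset.** Expected ratio = risk ratio × enrolment ratio r. With equal proportions it is simply r.

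**Illustration for clinic totals.** Assumptions: 14 clinics per arm; 150 participants per intervention clinic and 150/r per control clinic; equal proportion p; between-clinic CV 0.25; clinic-size CV c; unadjusted two-sided 5% test; random intercept only.

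- Var(log ratio) = [1/(150p) + r/(150p) + 2(0.25² + c²)] / 14
- Rejection = Φ(d − 1.96) + Φ(−d − 1.96), with d = ln r / SE

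Example, p = 0.06, c = 0, r = 1.2: variance (0.1111 + 0.1333 + 0.125)/14 = 0.0264; SE 0.162; d = 0.1823/0.162 = 1.12; rejection about 20%.

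Three checks stand beside the formula: a cluster-level t-test simulation (20,000 runs, p = 0.0605) with equal clinic sizes, the same with size CV 0.4, and a random-intercept Poisson fit (600 data sets per setting, p = 0.06, equal sizes within arm, Monte Carlo SE 0.8-1.8 points).

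| r | Formula, p 6-7.5%, c 0-0.3 | t-test, equal sizes | t-test, size CV 0.4 | Poisson, no offset | Poisson, log(n) offset |
|---|---|---|---|---|---|
| 1.00 | 5.0% | 4.8% | 5.0% | 5.7% | 5.7% |
| 1.05 | 5.7-6.3% | 6.4% | 5.2% | 4.3% | 4.7% |
| 1.10 | 7.7-9.8% | 8.6% | 6.8% | 10.8% | 5.7% |
| 1.20 | 15.1-22.6% | 19.0% | 12.0% | 24.7% | 6.7% |

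With clinic denominators in the t-test simulation, rejection stayed at 4.6-5.3% up to r = 1.5. The small Poisson simulation reads slightly above the formula at r = 1.10 and 1.20. The Wald test may account for part of that, since it gave 6.7% with the offset at r = 1.20.

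In events, 14 × 150 × 0.06 = 126 successes in the intervention arm against 126/r in control. That is 6, 11 or 21 extra successes at r = 1.05, 1.10 or 1.20 from enrolment alone.

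**The case against.** **Participant rows are the more natural reading.** SAP 2.1 treats the outcome as binary, SAP 4.3 says binary outcomes are analysed in the same way as the primary, four of the five named covariates belong to persons, and the Protocol calls the analysis individual-level. This carries real weight, but it does not settle the matter. SAP 2.1 has a separate null on the number, SAP 4.2 has a separate model for the proportion, and the SAP change history describes the Poisson model as being for absolute numbers of patients. The latest revision removed a per-month wording, and the current text states no exposure.

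**The rejection figures are not for the SAP's own model.** This stands. One row per clinic cannot carry the random slope, and no figure has been worked out for clinic-period rows. The figures show the mechanism only.

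**Large imbalance is unlikely.** Clinics are balanced on size, the Protocol synopsis aims for up to 150 per clinic, and enrolment is monitored by arm. This also stands. The only imbalance the documents name is the 5% trigger, where the effect is negligible. None of these measures enters the model, however.

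**Rejecting on unequal enrolment is not an error against a null about numbers.** That is literally true. It is then not an effect on diagnosis and treatment among enrolled patients, and the SAP should say which question it means.

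**A reader might infer that the mislabelled ratio biases the cost-effectiveness ratio.** SAP 4.3 takes its effectiveness term from the primary outcome, but no section converts the Poisson ratio as though it were an odds ratio. The documents do not support a figure for such a bias.

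**Conclusion.** The odds-ratio label on the Poisson result is wrong whatever the row unit. The error is about 4% at the planning values and has no effect on the test.

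The missing row unit and offset are a genuine gap in the specification of a formally tested primary hypothesis. Their consequence is conditional. It is nil with participant rows. With clinic totals it is about 6% rejection at a 5% imbalance, not distinguishable from nominal in simulation. At 10% and 20% it is about 7-10% and 12-23%, depending on an assumed clinic-size CV of 0-0.4. Those larger imbalances and the size CV are assumptions, and the figures leave out the recruitment-time slope and the Benjamini-Hochberg adjustment of SAP 4.1.

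A reader might go further and infer that the primary analysis as a whole has an inflated error rate. The documents do not support that. The binomial model for the proportion, on which the sample size rests, is unaffected, and aggregated rows are only one of two possible readings.

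**What to change.** Before database lock, in SAP 4.2:

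1. Report the exponentiated Poisson coefficient as a rate or risk ratio, and keep the odds ratio for the logit model. Express the number null in SAP 2.1 on the same scale.
2. State what one row of the count model is. If it is a participant, say so; no offset is needed.
3. If rows are aggregated, add the log of the number of participants analysed in that row as an offset. Use log clinic-time instead if yield per unit time is the stated question. Do not rely on the recruitment-time random effect in its place.
4. Apply the same to the secondary counts under SAP 4.3 that are formally tested. SAP 2.2 already exempts the ongoing-treatment number.

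The cost is a few sentences, with no change to endpoints or data collection. The one drawback is that with a log(n) offset the count test largely repeats the proportion test. The raw number is still reported.

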4.3 Analysis of the secondary outcomes

Diagnosis, treatment, and morbidity related endpoints

The analysis of the binary outcomes will be performed in the same way as the analysis of primary outcomes using GLMMs with Poisson or binomial distributions, for count or proportion data respectively.

Time-to-event analyses will be performed using mixed-effect Cox proportional hazards (PH) regression models (*coxme* package, *coxme* function in R). Kaplan Meier curves will be used to graphically represent the data. The possibility of non-proportional hazards will be assessed using Schoenfeld individual test and its graphical representation.

In case of non-proportional hazards, we will consider to split the time, use an interaction term, use a complementary log-log generalized linear model, or a combination of these approaches. If non-proportional hazard is caused by a confounder, we may set that variable as a strata.

As for primary outcome, the models will be adjusted for gender, age, HIV status, country, and asset index that is described below. In case of necessity, the models may be adjusted for the setting (i.e. urban, rural, peri-rural nesting the clusters), and site.

Direct cost and productivity, modelled cost, and cost effectiveness related endpoints:

MSeveral of these endpoints are not estimated using standard statistical analyses, but rather reflect descriptive analyses or model-based analyses that are not purely statistical in nature.

Patients' costs related to care

Patient costs will be estimated as the mean cost per patient interviewed. These costs will include direct and indirect costs incurred because of TB diagnosis. Direct costs will include all medical (including consultation fees and any out-of- pocket payment for medicines, X-rays, and diagnostics) and non-medical expenses (including travel costs of participants and caregivers,

QMS Form number: FM-06-02-	CONFIDENTIAL	Page 15 of 26
05/v2.0		_

FIND >>>	Statistical Analysis Plan		
Protocol number:	TB041-3/1-TAN / -MOZ		
Document version:	5.0	Document date:	11-JUL-2023

food costs incurred while in hospital, money spent buying any special foods). Indirect costs will be estimated as the opportunity cost of time spent seeking care (from the time of symptom onset to the time of treatment initiation), plus any lost productivity due to illness. Additional information from the scientific literature will be used to estimate costs that are not directly estimated (e.g., hospitalization costs, costs of TB treatment).

The total cost for each patient will be estimated as the sum of direct and indirect costs, and the mean cost will be taken as the sum of these total costs, divided by the number of patients.

Number of lost working days

We will use patient interviews to record the self-reported number of working days lost due to TB illness in both arms. This will be directly estimated; no additional statistical methods will be used. 95% confidence intervals will be calculated assuming a Poisson distribution.

Monthly earnings

To estimate loss in income, we will record the number of missed working days or missed working hours owing to TB illness, from the time of symptom onset to the time of treatment initiation. This number of days/hours will be multiplied by the average daily/hourly wage of employed laborers in each country to estimate the monthly earnings lost as a result of seeking care. If the patient does not have formal employment but works informally, e.g., as an agricultural worker, we will use their self-reported reduction in productivity (as a percentage of total productivity) over the course of the past year. This number will be multiplied by the average agricultural wage/earnings in each country and reported on a monthly basis. We will then calculate the mean monthly earnings lost as the sum of lost income (as described above), divided by the number of participants from which those data are obtained.

• Unit costs of diagnosis and treatment, modified societal perspective

We will estimate the health system cost per participant tested for TB on-site via the novel Molbio Truenat MTB/RIF platform versus the hub-and-spoke standard of care, predominantly off-site testing with Xpert MTB/RIF (Cepheid, Inc., Sunnyvale, CA, USA). These include cost for equipment, staffing, consumables, training, communication, and monitoring and evaluation. We will estimate ranges for health service delivery costs using trial expense reports, facility assessments, and project staff interviews. We will refer to existing scientific literature, information from facility assessments, expense reports, and project staff interviews to estimate the health system cost per patient treated.

Our modified societal perspective will include both health system costs (outlined in the paragraph above) and patient costs (as outlined earlier). Health system costs and patient costs will be summed on an individual basis to generate an estimate of the per-patient cost of diagnosis and treatment. This value will be estimated as a mean across all participants providing these data. Health system costs will be divided by the total number of participants at each site. We will report this outcome both by site and by country. Incremental cost-effectiveness ratio, modified societal perspective

QMS Form number: FM-06-02-	CONFIDENTIAL	Page 16 of 26
05/v2.0		-

FIND >>>	Statistical Analysis Plan		
Protocol number:	TB041-3/1-TAN / -MOZ		
Document version:	5.0	Document date:	11-JUL-2023

This quantity will be estimated as the incremental cost of the intervention (cost of intervention minus cost of standard of care), divided by the incremental effectiveness (i.e., incremental number of people diagnosed and treated in the intervention versus the standard of care). As above, a modified societal perspective will be used for both costs and effectiveness. The cost component of this equation will be estimated as described in the "unit costs" section above; the effectiveness component will be estimated as described for the primary outcome above. We will estimate uncertainty in this quantity using a simulation approach, where we draw independent simulations from the distribution of the primary outcome as inferred from the 95% confidence interval of the primary effectiveness outcome, as well as from the distribution of unit costs based on the empiric distribution of unit costs from our measurements above. We will report 95% uncertainty intervals as the outcomes falling within the smallest area covering 95% of the simulated costs and effectiveness values, plotted on a cost-effectiveness plane. We will perform these analyses separately by country.

BIA and ECEA of TB diagnostic tools.

Benefit incidence analysis (BIA) will be applied to assess the distribution of benefits of novel Molbio Truenat MTB/RIF platform (Int 1) compared to the hub-and-spoke standard of care (Int 0) and the centralized approach (Int 2). To conduct the analysis, data on health service utilization and unit costs for each strategy, categorized by socio-economic groups, will be estimated. Health service utilization rate will be estimated from the trial and expressed as the number and proportion of TB detected and started on treatment across each strategy and stratified by quintile (i.e., which indicates the extent to which the investments made in each diagnostic are allocated equitably, not considering only point of diagnosis, but also returning for test results, treatment initiation and any other needed follow up). The cost incurred by the public sector providers will be derived from the data gathered on unit cost of each diagnostic strategy. Regarding the SES status, a simplified asset indices adopted from standardized Equity Tool (https://www.equitytool.org/) is used to collect data on asset ownership (i.e., presence of a refrigerator, a mobile phone, a television, electricity, type of toilet, water supply, cooking fuel, and materials of the wall and floor) of study participants and a standardized scoring of these questions will be used to assign a wealth quintile for each respondents. Then health service utilization rate will then be multiplied by the unit costs of each diagnostic Intervention. The benefits of each diagnostic strategy utilization will be aggregated and expressed in monetary terms. Concentration curves and indexes will be computed to illustrate the extent of inequality in the distribution of health spending across quintile.

Extended cost-effectiveness analysis

Extended cost-effectiveness analysis will be used to estimate the additional financial protection offered by each diagnostic strategy (i.e., factoring benefit of early diagnosis, treatment initiation and productivity/income losses). Based on the results of the cost and cost-effectiveness analysis, it is important to check or observe variations in a decrease in out-of-pocket expenses (OOP) and indirect costs across the diagnostic strategies at a descriptive level. Once evaluated, the financial risk protection (FRP) benefits brought by each diagnostic intervention to households were measured based on the reduction in out-of-pocket expenditure (OOP) on average and across quintiles. First, the total OOP (i.e., both direct and indirect costs) for novel Molbio Truenat MTB/RIF platform, the hub-and-spoke standard of care and the centralized approach will be estimated.

QMS Form number: FM-06-02-	CONFIDENTIAL	Page 17 of 26
05/v2.0		-

FIND >>>	Statistical Analysis Plan			
Protocol number:	TB041-3/1-TAN / -MOZ			
Document version:	5.0	Document date:	11-JUL-2023	

Second, the total private expenditure averted will be estimated as the difference between the total OOP under each strategy from the base-case.

